To compare the detection of clinically significant cancer biopsy with systematic vs. MRI-targeted biopsy, stratified by transperineal vs. transrectal, the analyses will be conducted separately for the prior negative biopsy and active surveillance cohorts separately. For the prior negative biopsy patients, we will create a model with the outcome of clinically significant cancer and predictors of the linear predictor from the standard Prostate Biopsy Collaborative Group model plus PI-RADS version 2 MRI score and MRI prostate volume.⁵⁰ For the active surveillance cohort, we will use a similar approach but use the Canary "base" model for biopsy outcome in active surveillance patients.⁵¹ We will report the increase in discrimination associated with using MRI volume and PI-RADS score and conduct decision curve analysis, a decision-analytic technique that weighs the value of avoiding unnecessary biopsy compared to missing high-grade cancer, to assess the clinical utility of the models.⁵²

References

4. Litwin MS, Tan H-J. The diagnosis and treatment of prostate cancer: A review. *JAMA.* 2017;317(24):2532-2542. doi:10.1001/jama.2017.7248

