For the REDCap randomization model, randomization of subjects will occur on the data collection form where the randomization field is located. Before a subject is randomized, a 'Randomize' button will appear next to that field. When a user (who has been given appropriate 'Randomize' user privileges) clicks that button, a pop-up box will appear that will allow the user to randomize the subject. After a subject has been randomized, the grouping (i.e. transrectal or transperineal biopsy) will become permanently locked and unmodifiable. The randomization field will always be locked and unmodifiable both before and after randomization has occurred for a subject.

Randomization is unblinded, and research coordinators of respective enrolling sites will inform their patients of the assigned cohort.

Subjects randomized to TR-Bx will receive transrectal biopsy. Subjects randomized to TP-Bx will undergo a second consent discussion with the enrolling investigator, where the risks and benefits of transperineal biopsy will be explained. Subjects can then decide whether to undergo standard transrectal biopsy or transperineal biopsy. Subjects who agree to undergo TP-Bx will sign the second-stage consent form.

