4.5 Biopsy Procedure

A meeting of study investigators will take place before recruitment to review and ensure standardization of biopsies approaches. Investigators will follow the technique described by Kubo et al. to administer lidocaine during TP-Bx.²⁰ For both transperineal and transrectal approaches, 20 mL of 1% lidocaine will be used, respectively, to standardize local anesthesia. At each site, however, the choice of commercial MRI-targeted biopsy platform will be left to the physicians' discretion.

In both transperineal and transrectal biopsy arms for MRI-targeted biopsy, the number of systematic biopsy cores will be standardized to 12 cores. The technique for TR-Bx is performed as described by Kasivisvanathan et al.²² A total of 12 systematic biopsy cores will be obtained from the peripheral zone of the prostate at the base, mid gland, and apex. Locations of the 12 systematic cores are: Right lateral base, Right lateral midgland, Right lateral apex, Right medial base, Right medial midgland, Right medial apex, Left lateral base, Left lateral midgland, Left lateral apex, Left medial base, Left medial midgland, and Left medial apex. The technique for TP-Bx is performed as described by Urkmez et al.³⁸ Locations of the systematic cores will be obtained as follows: 2 cores each at Right posterior lateral, Right posterior medial, Left posterior lateral, and Left posterior medial, as well as 1 core each at Right anterior lateral, Right anterior medial, Left anterior lateral, and Left anterior medial.

In both transperineal and transrectal biopsy arms, the number of targeted biopsy cores will be standardized to 3 cores per target, with a maximum of three ROIs permitted to be chosen for targeted biopsy. MRI-targeted biopsy registration (i.e., matching of the image of the target on MRI with the real-time image of the prostate during biopsy) may be performed by means of visual registration or software-assisted registration.

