5.1 Adverse events

The primary objective of this study is to compare the incidence and severity of infectious complications experienced by patients undergoing TP-Bx versus TR-Bx. Patients will be assessed for complications by way of electronic questionnaire administered 7 ± 2 days post biopsy using a REDCap site hosted at Weill Cornell Medical Center. For patients unable to complete the questionnaire electronically, responses will be obtained via telephone interview. Any patient indicating that they experienced an adverse event will be contacted by the study team to seek further details. Additionally, all relevant medical records will be requested. Adverse events will be classified in accordance with Common Terminology Criteria for Adverse Events (CTCAE) v5.0.

The primary outcomes are infection rates of TP-Bx versus TR-Bx.

The secondary outcomes are patient-reported pain and anxiety, and comparison of noninfectious complications such as bleeding and urinary retention rates, and cancer detection.

Timing for assessment of study variables.			
Assessment	Baseline Pre-Bx	Day of Bx	7-days Post-Bx
Baseline history and physical exam, screening, consent	✓		
Prior Bx (Y/N)	✓		
Prior Bx infection (Y/N)	✓		
PSA	✓		
Indication for Bx	✓		
MpMRI findings	✓		
Randomization: TR-Bx vs. TP-Bx	✓		
Bx infection risk determination for TR-Bx prophylaxis	✓		
Bx completed (Y/N)		✓	
Bx duration (minutes)		✓	
Pain (VAS)		✓	✓
Discomfort (VAS)		✓	✓
TMI Anxiety (Likert 5 levels)		✓	
Decision regret			✓
Adverse events (Y/N) and Bother			
UTI			✓
Sepsis			✓
Urinary retention			✓

Fever	✓
Hematuria	✓
Hematochezia	✓
Hematospermia	✓
UTI diagnosed by HCP	✓
Unplanned HCP contact	✓
Qualitative responses	✓
Bx pathologic outcomes, if cancer:	✓
Gleason grade group(s)	✓
Number of cores positive	✓
Number of cores negative	✓
Maximum cancer core length	✓
Targeted Bx positive (Y/N/NA)	✓
Systematic Bx positive (Y/N)	✓
Location of positive cores	✓

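### Section 6 sets out to compare systematic with MRI-targeted detection of Grade Group ≥2 cancer, but the only method it gives is a risk model that does not estimate that contrast

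*Combined protocol and SAP*

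**What the plan says.** The final paragraph of Section 6 opens with the aim: "To compare the detection of clinically significant cancer biopsy with systematic vs. MRI-targeted biopsy, stratified by transperineal vs. transrectal". It asks for separate analyses in the prior-negative and active-surveillance cohorts.

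For prior-negative men the method is: "we will create a model with the outcome of clinically significant cancer and predictors of the linear predictor" of the Prostate Biopsy Collaborative Group calculator, with PI-RADS score and MRI prostate volume added. Active-surveillance men get the same construction on the Canary base model. The reporting is: "We will report the increase in discrimination associated with using MRI volume and PI-RADS score", together with decision curves that judge the usefulness of the models.

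Four other places bear on the point:

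- **Section 4.5** fixes the sampling: "In both transperineal and transrectal biopsy arms for MRI-targeted biopsy, the number of systematic biopsy cores will be standardized to 12 cores", and "the number of targeted biopsy cores will be standardized to 3 cores per target", with at most three regions targeted.
- **Section 5.1**, timing table, has one positivity flag for targeted cores (with a not-applicable level) and another for systematic cores. It also lists Gleason grade group(s) and the location of positive cores.
- **Section 5.3 and the earlier part of Section 6** compare cancer detection between the transperineal and transrectal approaches.
- **Section 1 and the Protocol Summary** list cancer detection as a secondary objective, again by approach.

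**The concern.** The aim and the method answer different questions. The aim asks which kind of core finds clinically significant cancer in a man who has both. The method asks how well a risk score, with and without MRI information, predicts that a man has such cancer.

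This goes beyond missing detail, because the analysis that is named does not fit the aim it is attached to. If the comparison is reported, several choices would have to be made after the data are in: Grade Group ≥2 or any cancer, how to treat men with no target, paired or unpaired analysis, and what interval to give. The two positivity flags in Section 5.1 suggest that the comparison is intended, yet no stated analysis uses them.

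**Working it through.** The plan gives no sample size, effect or error rate for this contrast, so there is no figure to reproduce.

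**1. Scope.** From Section 6: 620 prior-negative + 682 active-surveillance = 1,302 men, and 1,302 / 1,702 = 76.5%. This is a ceiling, because men without an MRI target cannot contribute. MRI is expected in these cohorts: Section 3.3 excludes previously biopsied men who have a contraindication to it.

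**2. Aim and method side by side.**

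| Element | Needed for the aim | Given in Section 6 |
|---|---|---|
| Outcome | Grade Group ≥2 in targeted cores; Grade Group ≥2 in systematic cores | Clinically significant cancer, one outcome per man |
| Contrast | Targeted minus systematic, within man | None by core type |
| Predictors | None needed for a paired difference | Risk score, PI-RADS, MRI volume |
| Output | Difference in detection with interval | Gain in discrimination, decision curves |
| Approach | Results by approach | No approach term in the models described |

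Fitting the models separately by approach would fill the last row only.

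**3. Do other sections supply a method?** Section 5.3 compares detection by approach. The logistic regressions and risk differences in Section 6 are for transperineal versus transrectal, and the interaction models ask whether that effect varies by race or diagnostic setting. None is by core type.

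**4. Illustration.** Assume 310 simulated men, 90 of them with Grade Group ≥2 in at least one core, and simulated covariates. Keep each man's any-core status and covariates fixed and change only which core type found the cancer. Let b be the number of men positive on targeted cores only, and c the number positive on systematic cores only; 38 are positive on both. Then:

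- difference = (b − c) / n
- SE = √[(b + c) − (b − c)²/n] / n
- 95% CI = difference ± 1.96 × SE

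| Scenario | b, c | Targeted, systematic | Difference (95% CI) | Exact McNemar p | AUC, base to with MRI |
|---|---|---|---|---|---|
| Targeted better | 36, 16 | 23.9%, 17.4% | 20/310 = +6.5 points (1.9 to 11.0) | 0.008 | 0.7435 to 0.8144 |
| Equal | 26, 26 | 20.6%, 20.6% | 0/310 = 0.0 points (−4.6 to 4.6) | 1.0 | 0.7435 to 0.8144 |
| Systematic better | 13, 39 | 16.5%, 24.8% | −26/310 = −8.4 points (−12.8 to −3.9) | 0.0004 | 0.7435 to 0.8144 |

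For the first row, SE = √(52 − 400/310)/310 = 0.0230. The model output, including the PI-RADS coefficient of 0.725, is the same in all three rows, although the contrast runs from +6.5 to −8.4 points. The sizes are invented. The sameness is structural: with an any-core outcome, the model never sees core type.

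**5. Is the paired analysis feasible?** Yes. Section 4.5 gives both core types in the same man, in both arms, whenever a target is sampled.

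**The case against.** The strongest reply is that the opening sentence is itself a commitment. It names the contrast, the strata and the cohorts, and Section 5.3 defines clinically significant as Grade Group ≥2. On that reading a descriptive comparison of detection proportions is understood, and the models are a second analysis of the value of MRI. This stands in part: the plan does not rule the comparison out. But the models are introduced as the way to carry out the aim, and no estimator, population or interval is written for the comparison anywhere.

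A second reply is that the model outcome is not said to be cancer in any core, so the simulation fixes something that the text leaves open. That is fair, and the simulation illustrates only that reading. Still, nothing says the models would be fitted by core type. A single model with a targeted-only or systematic-only outcome would also report discrimination rather than a difference in detection.

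A third reply concerns approach. A reader might take the undefined strata as a fault of this analysis. Under two-stage consent, men randomized to transperineal biopsy have a choice: "Subjects can then decide whether to undergo standard transrectal biopsy or transperineal biopsy". So as-performed and as-randomized strata can differ. But that question touches every analysis by approach, and one-stage consent is also allowed. Here it is only a detail to state.

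**Conclusion.** The point holds in a limited form: Section 6 specifies no method that estimates its stated contrast between systematic and MRI-targeted detection. This rests on reading the model outcome as one patient-level status, which is how it is written, and on finding no core-type analysis elsewhere in the document.

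Three stronger readings are not supported:

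- **That the trial can produce no such estimate.** The sampling in Section 4.5 is paired, and the comparison is feasible. What is missing is the specification.
- **That the data fields cannot give Grade Group ≥2 by core type.** The flags in Section 5.1 are for any positive core, but the same table lists grade group(s), possibly more than one, and the location of positive cores. The document does not say that a single overall grade is kept. This needs confirming; it is not a demonstrated gap.
- **That the main results are at risk.** The contrast is not a listed objective. The primary infection result and the comparison of detection between approaches do not depend on it.

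This is an improvement to consider, and confidence in the mismatch is high.

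**What to change.** Split the final paragraph of Section 6 into two aims.

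1. **Core-type comparison, labelled supplementary.** In prior-negative and active-surveillance men with at least one MRI target and both core types sampled, report the within-patient difference in Grade Group ≥2 detection (targeted minus systematic) with a 95% CI, with McNemar's test as support. Give results by cohort and by approach, and state whether approach means as performed or as randomized. Men without targeted cores can be identified from the not-applicable level of the existing field.
2. **MRI-based risk prediction.** Keep the risk-score plus MRI models, discrimination gain and decision curves as they are, under their own aim.

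Confirm that grade group is abstracted separately for targeted and systematic cores, and add the field if it is not.

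If no core-type comparison is intended, rewording the opening sentence as MRI-based risk prediction would be enough.

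The cost is SAP wording, one small analysis and possibly one or two abstraction fields taken from pathology reports. No new procedures or visits are needed.

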APPENDIX

Immediate post biopsy questionnaire

Please ask the patient to fill this out after the biopsy, before they leave the department.

Please check the box corresponding to the number, which describes how you felt immediately after the biopsy procedure:

1. Overall, how much **discomfort** did the biopsy procedure cause you?

2. Overall, how much **pain** did the biopsy procedure cause you?

A horizontal scale with numerical labels from 0 to 10. The scale is divided into 11 equal segments. Below the scale, the labels are: 'No pain' under 0, 'Moderate pain' under 5, and 'Extreme pain' under 10.

3. Overall, how much **fear/anxiety** did the biopsy procedure cause you?

Did you experience the following problems during the 7 days after the biopsy procedure?

1. Fevers

Yes

No

2. Shivering and/or chills, as if you had a flu

Yes

No

3. Blood in the urine ("pee")

Yes

No

4. Blood in the semen (ejaculate or "cum")

Yes

No

5. Blood in the stools ("poop")

Yes

No

6. Acute urinary retention, meaning being unable to pass urine ("pee") which was relieved by putting a catheter into the bladder through the penis

Yes

No

7. Urinary tract infection diagnosed by a healthcare professional (doctor or nurse)

Yes

No

8. Please list any new medications, especially any painkillers or antibiotics, that you have taken since the biopsy. Do not list your regular medications but do list any new medications started related to the biopsy. Only list the medications if you have taken them. An example is given in the first box:

Name of medication	Dosage	Number of doses per day	Number of days
--------------------	--------	-------------------------	----------------

e.g. ciprofloxacin	500mg	2	3

9. Since the biopsy, have you had contacts with hospital services for reasons related to the biopsy, which were unplanned and not part of the routine study visits?

Please answer yes if you have had any unplanned contact with any healthcare staff e.g. doctor, nurse, other. Please also answer yes if you have had any unplanned consultations with healthcare staff over the phone:

Yes

No

10. Since the biopsy, have you had contacts with the community healthcare team for reasons unrelated to the biopsy?

Please answer yes if you have had any contact with any healthcare staff in the community e.g. GP, practice nurse, community nurse, other. Please also answer yes if you have had any consultations with community healthcare staff over the phone:

Yes

No

Thank you for completing the questionnaire. Please contact us if you have any questions.
